6.2.1. Analysis of Efficacy Endpoints of Interest

The number and percentage of participants in each clinical status category for each day from Baseline through Day 14 and at Day 28 and using the last available assessment will be summarized by group. These results will be summarized using (1) the clinical status definition in Section 6.2 and (2) with the definition specified in Section 6.2 but excluding days with missing ordinal scale score not due to death or discharge alive. In addition, stacked bar charts by study day (Baseline through Day 14 and at Day 28) will be produced by group using the definition specified in Section 6.2.

The number and percentage of participants in each clinical status category for each day from Baseline through Day 14 and at Day 28 and last available assessment will be summarized within each subgroup defined in Section 3.4.1.

The change from baseline in clinical status category on Days 5, 7, 11, 14, 28 and last available assessment will be summarized by group using descriptive statistics.

Number of days of oxygen support status modes (invasive mechanical ventilation, high flow oxygen, low flow oxygen) will be calculated as the number of days oxygen support was reported on the 7-point ordinal scale eCRF through death, discharge alive, or Day 14 and presented for each group using descriptive statistics.

A shift table of baseline oxygen support status (death, invasive mechanical ventilation, high flow oxygen, low flow oxygen, room air, discharge alive) to Days 5, 7, 11, 14, 28 and the last available status will be provided for each group.

Duration of hospitalization will be calculated only for participants who are discharged alive on or prior to Day 28 and will be summarized for each group using descriptive statistics.

All-cause mortality will be estimated for each group using the Kaplan-Meier product limit method with all available data. Participants who did not die will be censored at the last study day.

Days to clinical improvement and days to recovery will be estimated for each group using a competing risk analysis approach, with death as the competing risk. Participants without recovery will be censored on the day of the last non-missing ordinal scale assessment.

Forest plots by subgroup will be presented for all-cause mortality Kaplan-Meier estimates on Day 28 and cumulative incidence of recovery on Day 28.

The number and percent of participants in each group with ≥ 1 -point improvement, ≥ 2 -point improvement, and recovery will be presented with 95% confidence intervals on Day 5, Day 7, Day 11, Day 14, Day 28 and last available assessment.

Analyses will be performed using the Expanded RDV-Treated Analysis Set.

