6.5. Day 28 Follow up Assessment (±5 Days)

The following evaluations are to be completed if this visit is conducted in person. For participants who have been discharged from hospital, the final evaluation can be made by phone. Only AE and concomitant medication and ordinal scale (if discharged on or after Day 14) review are to be completed if visit is conducted by phone.

- Physical examination and vital signs (heart rate, temperature, blood pressure)

- Documentation of respiratory status:

Respiratory rate

- Oxygen supplementation: room air, low flow O₂ (L/min and %), high flow O₂ (L/min and %), CPAP/BIPAP (FiO₂ or %), mechanical ventilation (FiO₂ or %), ECMO

Oxygenation: SpO₂ or PaO₂

Radiographic findings (if available)

- Review AEs and document concomitant medications
- Review the Ordinal Scale (Section 6.9). If subject was not discharged by Day 14, any change in category and the date of any change in category from Day 14 to discharge (or Day 28) should be recorded

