6.10. Post-treatment Assessments

No assessments are required after Day 28.

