7.3.3. Serious Adverse Events

All SAEs, regardless of cause or relationship, that occurs after the subject first consents to participate in the study (ie, signing the informed consent) and throughout the duration of the study, including the protocol-required post treatment follow-up period must be reported on the applicable eCRFs and Pharmacovigilance an Epidemiology (PVE) as instructed below in this section. This also includes any SAEs resulting from protocol-associated procedures performed after informed consent is signed.

Any SAEs and deaths that occur after the post-treatment follow-up visit but within 30-days of the last dose of study drug, regardless of causality, should also be reported.

Investigators are not obligated to actively seek SAEs after the protocol-defined follow-up period; however, if the investigator learns of any SAEs that occur after the protocol-defined follow-up period has concluded and the event is deemed relevant to the use of study drug, the investigator should promptly document and report the event to Gilead PVE.

All AEs and SAEs will be recorded in the eCRF database within the timelines outlined in the eCRF completion guidelines.

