3.8. Analysis Visit Windows

3.8.1. Definition of Study Day

Study Day 1 is defined as the first dosing date of study drug.

Study Days are calculated relative to Study Day 1 and derived as follows:

- For postdose study days: Assessment Date – First Dosing Date + 1
- For days prior to the first dose: Assessment Date – First Dosing Date

Therefore, **Study Day 1/ First Dose Date** is the day of first dose of study drug administration, as recorded on the Study Drug Administration eCRF form.

Last Dose Date is defined as the maximum, nonmissing, nonzero dose end date of treatment recorded on the Study Drug Administration eCRF form with “Study Drug Permanently Withdrawn” box checked for participants who prematurely discontinued or completed study drug according to the Study Drug Completion eCRF. Refer to [Appendix 2](#) for missing date imputation, if necessary.

Last Study Date is the latest of the study drug start dates and end dates, the clinic visit dates, and the laboratory visit dates, including the 28-day follow-up visit date, and the death date (if applicable, only for participants who prematurely discontinued study according to the Study Completion eCRF).

Baseline value is defined as the last value obtained on or prior to the first dose date (and time, if available) unless otherwise specified (see Section [3.8.3](#)).

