Hematology	Hemoglobin (g/dL)	1
Hematology	Hematocrit (%)	1
Hematology	Platelet count (x10 ⁹ /L)	0
Hematology	WBC (x10 ⁹ /L)	2
Chemistry	ALT (U/L)	0
Chemistry	AST (U/L)	0
Chemistry	Total bilirubin (mg/dL)	2
Chemistry	Glucose (mg/dL)	0
Chemistry	Serum creatinine (mg/dL)	2
Chemistry	Creatinine Clearance by Cockcroft Gault (mL/min)	1

Standard deviation and standard error will be reported to one more significant decimal place than the raw measurement.

Mean, median, minimum, Q1, Q3, and maximum will be reported to the same number of decimal places of the raw measurements.

Exceptions may be considered; for example, if more than 4 significant digits are provided for the measurement.

- 14) Last dose date is not expected to be missing. However, if last dose date is missing, it will be imputed using the maximum of non-missing, non-zero dose, study drug start and stop dates.
- 15) Incomplete death dates will be imputed as the maximum of the study drug start dates (lasfdt), study drug end dates (lasldt), clinic visit dates (lvis28dt), laboratory visit dates (llab28dt), including the 28-day follow-up visit date plus 1, ie dthdt
 $\max(\text{lasfdt}, \text{lasldt}, \text{lvis28dt}, \text{llab28dt}) + 1$.
- 16) Ordinal scale and oxygen support status

The oxygen support status is derived from the ordinal scale:

Ordinal Scale		Oxygen Support Status
1	Death	Death
2	Hospitalized, on invasive mechanical ventilation or ECMO	Invasive Mechanical Ventilation
3	Hospitalized, on non invasive ventilation or high flow oxygen devices	High Flow Oxygen
4	Hospitalized, requiring low flow supplemental oxygen	Low Flow Oxygen
5	Hospitalized, not requiring supplemental oxygen requiring ongoing medical care (COVID 19 related or otherwise)	Room Air
6	Hospitalized, not requiring supplemental oxygen no longer requires ongoing medical care (other than per protocol RDV administration)	Room Air
7	Not hospitalized	Discharge

17) Censoring rules

Time to death: participants are censored at the last known date alive (last study day)

Time to ≥ 2 -point improvement, time to ≥ 1 -point improvement, time to recovery; if a participant does not experience the event of interest and does not die, the participant is censored at the last non-missing ordinal scale assessment date.

18) Graded Laboratory Abnormalities Summary

The following labels will be used for laboratory abnormalities and Grade 3 or 4 laboratory abnormalities summary tables and listings:

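### Kaplan-Meier mortality in Part B counts deaths reported after the follow-up visit but censors survivors at it: the Day 28 value is slightly too high, and any later value is unreliable.

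*SAP*

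**What the plan says.** **Endpoint.** Protocol 3.1 sets the endpoint as mortality at Day 28. SAP 6.2 lists all-cause mortality with no day attached, and SAP 6.3 declares no changes from the protocol's efficacy analyses.

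**Estimator and censoring.** SAP 6.2.1: "All-cause mortality will be estimated for each group using the Kaplan-Meier product limit method with all available data". It continues: "Participants who did not die will be censored at the last study day". Appendix 2 item 17 repeats the rule, equating the last study day with the last date known alive.

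**Last study date.** SAP 3.8.1: "Last Study Date is the latest of the study drug start dates and end dates, the clinic visit dates, and the laboratory visit dates". The follow-up visit is included. The death date is included as well, but "only for participants who prematurely discontinued study according to the Study Completion eCRF".

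**Follow-up.** Protocol 6.5 allows the Day 28 contact 5 days either way, so Days 23 to 33, by phone if the participant has been discharged. Protocol 6.10 adds: "No assessments are required after Day 28".

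**Late deaths.** Protocol 7.3.3 nevertheless makes these reportable: "Any SAEs and deaths that occur after the post-treatment follow-up visit but within 30-days of the last dose of study drug". Sites need not actively look for serious events after follow-up ends.

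**Output.** The only Kaplan-Meier mortality value that the SAP names is the Day 28 estimate, for the subgroup forest plots in 6.2.1.

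**The concern.** Kaplan-Meier needs censoring that carries no information about the outcome. Here the two outcomes have different observation windows. A survivor leaves the risk set at the follow-up visit. A participant with the same visit date who dies a week later stays in the risk set until death, because the death report extends that person's follow-up. The numerator keeps every reported death while the denominator loses the survivors, so the estimated daily hazard is too high from the first visits onwards.

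Part B has no randomised comparison and no formal testing (SAP 3.3). Each group's mortality is read as an absolute figure, and no between-arm contrast could cancel the bias. A larger sample does not reduce it either.

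**Working it through.** The documents give no expected mortality, event count or precision for this analysis, so there is no planned figure to reproduce. The check applies the stated rules to assumed mortality.

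**Inputs from the documents**
- Visits fall on Days 23 to 33 (Protocol 6.5).
- Survivors are censored at the visit (SAP 6.2.1, 3.8.1).
- Late deaths are reportable to last dose + 30 days: Day 10 + 30 = Day 40 for a full course (Protocol 7.3.3; SAP 1.2).

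**Assumptions (not in the documents)**
- Mortality by Day 22 is 8%, 10% or 25%, followed by a constant daily hazard *h* of 0.1%, 0.3% or 0.8% (low, middle, high).
- Visits are spread evenly over the window, and all late deaths to Day 40 are reported.

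**Formula.** Among those truly alive at the start of day *t*, let v = (34 − t)/11 be the share whose visit is on day *t* or later (v = 0 after Day 33). Let p = 1 − (1 − h)^(41 − t) be the chance of dying between day *t* and Day 40. The share counted as at risk is n = v + (1 − v)p, and the estimated daily hazard is h/n instead of h.

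**Middle scenario, Days 23 to 28**

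| Day | v | p | n | h/n |
|---|---|---|---|---|
| 23 | 1.000 | 0.053 | 1.000 | 0.300% |
| 24 | 0.909 | 0.050 | 0.914 | 0.328% |
| 25 | 0.818 | 0.047 | 0.827 | 0.363% |
| 26 | 0.727 | 0.044 | 0.739 | 0.406% |
| 27 | 0.636 | 0.041 | 0.651 | 0.461% |
| 28 | 0.545 | 0.038 | 0.563 | 0.533% |

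The estimate at Day 28 is 1 − 0.90 × ∏(1 − h/n) = 12.1%. The true value is 1 − 0.90 × 0.997^6 = 11.6%.

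**After Day 33.** Now v = 0, so n = p. On Day 34, p = 1 − 0.997^7 = 0.021 and h/n is about 14% in one day. On Day 40, p = h and h/n = 1, so estimated survival is zero.

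**Simulation of the same rules** (150 runs per scenario; low / middle / high)

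| Day | SAP rule | True |
|---|---|---|
| 28 | 8.8 / 12.1 / 29.6% | 8.6 / 11.6 / 28.5% |
| 33 | 10.8 / 17.7 / 39.4% | 9.0 / 12.9 / 31.3% |
| 40 | 100% in every run with n ≥ 1000 | 9.6 / 14.7 / 35.1% |

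**Sensitivity (middle scenario, n = 1000, unless stated)**
- *Visit timing.* With visits clustered near Day 28 (SD 2 days), Day 28 reads 11.8% against 11.5%, but Day 33 reads 26.6% against 12.9%. With every visit on Day 28, the Day 28 bias is zero and Day 33 reads 48.9% against 13.0%. Clustering helps the planned value and worsens the tail.
- *Survivors with later dates.* If 2%, 5% or 10% of survivors have a last study date on Days 34 to 45 (visits otherwise even), Day 40 reads about 69%, 49% or 36% against a true value of about 15%.
- *Partial reporting.* If 30% of late deaths are reported, Day 28 reads 11.8% against 11.6% and Day 33 reads 14.5% against 13.0%. In a group of 300 at low hazard, only 39% of runs then reach 100%.
- *Same cut-off for dead and alive.* Ending everyone's follow-up at his or her own visit gives 8.6 / 11.6 / 28.5% at Day 28 and 9.0 / 12.9 / 31.3% at Day 33, equal to the true values. This assumes that visit timing is unrelated to the risk of death.

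**The case against.** A reader might infer that the main mortality display for up to about 5600 participants will run to 100% mortality. The documents do not support that.

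- **No Kaplan-Meier plot and no time point after Day 28 is specified.** The named figures are stacked bars, forest plots and a cumulative incidence plot for the competing-risk endpoints. Deaths by Day 28 also appear in the clinical-status and shift tables. This stands. However, the estimation sentence has no time limit, so nothing prevents a full curve.
- **Reaching 100% is conditional.** It needs a reported death after the last survivor is censored, and no survivor with a later clinic or laboratory date. SAP 3.8.2 puts no upper limit on the Day 28 vital-sign window or the post-Day 14 laboratory window, so late dates are foreseen. Day 40 is also a maximum, because dosing stops at discharge. This stands; the tail is still far too high with a few late dates.
- **The planned readout moves little.** At about 20% mortality, 0.4% per day and even visits (all assumed), the Day 28 excess is about 0.6 points. It is about 0.25 if visits cluster near Day 28 (SD 1.5 days). The sampling SD is about 1.3 points at n = 1000. Extending the documents' only mortality assumption, 2% at Day 14 in Part A, gives 0.1 to 0.3 points. This stands, although sampling error shrinks with group size (√(0.2 × 0.8/4000) = 0.6 points at n = 4000) and the bias does not.
- **Late deaths might not be events at all.** SAP 3.8.1 counts the death date in the last study date only for participants who left the study early, so the handling of deaths after completion is partly unclear. But the censoring sentence covers only those who did not die. Appendix 2 item 15 also imputes incomplete death dates to one day after the latest study date. Counting them as events is the natural reading, and the ambiguity needs its own sentence.

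**Conclusion.** As written, the rules make censoring depend on the outcome and bias mortality upwards. Mechanism and direction follow from the documents; the size rests on assumed hazards, visit spread and reporting.

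- **Day 28, the value to be reported:** 0 to about +1 point, and 0 if all visits fall on Day 28.
- **After Day 28:** badly inflated in the scenarios with full reporting, and able to reach 100% after Day 33 under the two conditions above.

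Severity is minor to moderate: minor if only Day 28 values are shown, more if the curve or any later value is presented. A claim that the planned mortality result is seriously wrong, or that the curve must reach 100%, would go beyond the documents.

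**What to change.** In SAP 6.2.1 and Appendix 2 item 17:

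1. Replace the all-available-data wording with an analysis that ends at Day 28, the protocol endpoint, and give no estimate or plot beyond it.
2. End follow-up for every participant, dead or alive, at the earlier of Day 28 and the last direct contact: dosing, clinic or laboratory date, or follow-up visit, including by phone.
3. Leave the death date out of that definition, except for deaths during ongoing study follow-up (before the follow-up visit and before leaving the study), which remain events. Using Last Study Date as SAP 3.8.1 defines it would keep the asymmetry for early discontinuers, because for them it includes the death date.
4. State how deaths after study completion enter.
5. Add a Day 28 sensitivity analysis that counts all deaths reported by Day 28 and treats participants last seen on Days 23 to 27 with no death report as alive. It reads low if late deaths are under-reported, so a gap from the main estimate is informative.

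Stopping at Day 28 alone removes the false tail but leaves the small bias from early visits. Later deaths remain visible in the deaths listing and treatment-emergent death summary already planned in SAP 7.2.6.

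The cost is a few sentences and one extra analysis. The downside is that a few known deaths on Days 24 to 28 after an early visit move from the main estimate to the sensitivity analysis.

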6.3. Changes from Protocol-Specified Efficacy Analyses

There are no changes from the protocol-specified efficacy analyses.

7. SAFETY ANALYSES

Safety data will be summarized for the participants in the Expanded RDV-Treated Analysis Set. All safety data collected on or after the date that study drug was first dispensed through 30 days after last dose will be summarized by group for the Expanded RDV-Treated Analysis Set, unless specified otherwise. All safety data will be included in data listings.

7.1. Endpoint of Interest

The percentage of participants in the Mechanically Ventilated Treatment Group and the Extension Treatment Group with any treatment-emergent adverse events, an endpoint of interest, will be summarized for each group.

7.2. Adverse Events and Deaths

7.2.1. Adverse Event Dictionary

Clinical and laboratory adverse events (AEs) will be coded using MedDRA. SOC, high-level group term (HLGT), high-level term (HLT), PT, and lowest-level term (LLT) will be provided in the AE dataset.

7.2.2. Adverse Event Severity

The severity of AEs will be graded using the Division of AIDS (DAIDS) Table for Grading the Severity of Adult and Pediatric Adverse Events, Version 2.1 dated July 2017. For each episode, the highest grade attained should be reported as defined in the grading scale. The DAIDS scale is available at the following location:

<https://rsc.niaid.nih.gov/sites/default/files/daidsgradingcorrectedv21.pdf>

Adverse events are graded by the investigator as Grade 1 (mild), Grade 2 (moderate), Grade 3 (severe), Grade 4 (life threatening) or Grade 5 (fatal) according to toxicity criteria specified in the document above. The severity grade of events for which the investigator did not record severity will be left as “missing” for data listings.

7.2.3. Relationship of Adverse Events to Study Drug

Related AEs are those for which the investigator selected “Related” on the AE eCRF to the question of “Related to Study Treatment.” Events for which the investigator did not record relationship to study drug will be considered related to study drug for summary purposes. However, by-subject data listings will show the relationship as missing.

7.2.4. Serious Adverse Events

Serious adverse events (SAEs) will be identified and captured as SAEs if AEs met the definition of SAE specified in the study protocol. Serious adverse events captured and stored in the clinical

database will be reconciled with the SAE database from the Gilead Global Patient Safety (GLPS) before data finalization.

7.2.5. Treatment-Emergent Adverse Events

7.2.5.1. Definition of Treatment-Emergent Adverse Events

Treatment-emergent adverse events (TEAEs) are defined as 1 or both of the following:

- Any AEs with an onset date on or after the study drug start date and no later than 30 days after permanent discontinuation of study drug
- Any AEs leading to premature discontinuation of study drug.

7.2.5.2. Incomplete Dates

If the onset date of the AE is incomplete and the AE stop date is not prior to the first dosing date of study drug, then the month and year (or year alone if month is not recorded) of onset determine whether an AE is treatment emergent. The event is considered treatment emergent if both of the following 2 criteria are met:

- The month and year (or year) of the AE onset is the same as or after the month and year (or year) of the first dosing date of study drug, and
- The month and year (or year) of the AE onset is the same as or before the month and year (or year) of the date corresponding to 30 days after the date of the last dose of study drug

An AE with completely missing onset and stop dates, or with the onset date missing and a stop date marked as ongoing or on or after the first dosing date of study drug, will be considered to be treatment emergent. In addition, an AE with the onset date missing and incomplete stop date with the same or later month and year (or year alone if month is not recorded) as the first dosing date of study drug will be considered treatment emergent.

7.2.6. Summaries of Adverse Events and Deaths

The number and percentage of participants who experienced at least 1 TEAE will be provided and summarized by SOC, HLT, PT, and group. For other AEs described below, summaries will be provided by SOC, PT, and group using the Expanded RDV-Treated Analysis Set:

- Grade 3 or higher treatment-emergent AEs
- All treatment-emergent study drug-related AEs
- Grade 3 or higher treatment-emergent study drug-related AEs
- All treatment-emergent SAEs
- All treatment-emergent study drug-related SAEs

- All treatment-emergent AEs that caused premature discontinuation from study drug
- Treatment-emergent deaths

A brief, high-level summary of AEs described above will be provided by group and by the number and percentage of participants who experienced the above AEs. Treatment-emergent deaths observed in the study will also be included in this summary.

Treatment-emergent death refers to deaths that occurred between the first dose date and the last dose date plus 30 days (inclusive).

Multiple events will be counted only once per participant in each summary. Adverse events will be summarized and listed first in alphabetic order of SOC and HLT within each SOC (if applicable), and then by PT in descending order of total frequency within each SOC. For summaries by severity grade, the most severe grade will be used for those AEs that occurred more than once in an individual participant during the study.

In addition to the above summary tables, all treatment-emergent AEs, treatment-emergent AEs with Grade 3 or higher, treatment-emergent study drug-related AEs, treatment-emergent study drug-related AEs with Grade 3 or higher, and treatment-emergent SAEs will be summarized by PT only, in descending order of total frequency. Preferred terms with the same total frequency will be sorted in alphabetical order. Treatment-emergent AEs and study-drug related treatment-emergent AEs will also be summarized by highest grade.

Data listings will be provided for the following:

- All AEs
- Study-Drug-Related AEs
- AEs with severity of Grade 3 or higher
- SAEs
- Study-Drug-Related SAEs
- Deaths
- AEs leading to premature discontinuation of study drug

